### 6.2.3 Specimen Shipment

*Whole blood for immunologic phenotyping, genetic testing, and ex vivo assays by [name] collected at Harbor-UCLA* will be shipped at ambient temperature by Fed Express overnight, following International Air Transport Association (IATA) regulations (double package or bag all specimens; include an absorbent square in each bag; affix "Exempt Human Specimens" label to box). Ship for arrival within 36 hours of collection to:

[name]/[name]  
[name]  
[name]  
Minneapolis, MN [contact]

Contact [name] 48 hours in advance by Phone (above) or Email: [[contact]](mailto:[contact]) prior to shipping. Deliver before 10:30 am on Tuesday – Thursday.

Contact [name] by [contact] or email: [[contact]](mailto:[contact]) 48 hours prior to shipping.

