### ***Bone Biomarkers***

Samples for bone biomarkers will be stored at each site at -80°C until the end of the study at which time all samples will be shipped/transported on an adequate amount of dry ice to [name], Cytokine Reference Lab. For shipping samples to [name], samples will be shipped on an adequate amount of dry ice to the study PI following International Air Transport Association (IATA) regulations (double package or bag all specimens; include an absorbent square in each bag; affix "Exempt Human Specimens" label to box). Ship for arrival within 36 hours:

[name]

Cytokine lab  
[name]  
[name]  
[name]

Contact [name] 48 hours in advance by [contact] or email: [[contact]](mailto:[contact]). Deliver before 10:30 on Tuesday – Thursday.

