**APPENDIX B**

Schedule of Events (next page)

Schedule of Events										If ADA Positive	
	Screening a	Baseline	time from 1 st IFN- $\gamma$ 1b dose							time from last IFN- $\gamma$ 1b dose	
			3 weeks ( $\pm$ 2 days)	4 weeks ( $\pm$ 2 days)	6 weeks ( $\pm$ 2 days)	3 months ( $\pm$ 1 week)	6 months ( $\pm$ 1 week)	9 months ( $\pm$ 1 week)	12 months ( $\pm$ 1 week)	2-3 weeks	every 4-6 weeks
General											
Medical history	X	X				X	X		X		
Physical exam		X				X	X		X		
Genotype b		X									
RNA and DNA samples		X f				X	X		X		
Anthropometric measurements	X	X f				X	X		X		
Safety Measuresc											
Basic metabolic panel (BMP)	X	X		X	X	X	X	X	X		
Liver function tests (LFT)	X	X		X	X	X	X	X	X		
Urine pregnancy test (UPT) e	X	X				X	X	X	X		
Urinalysis (UA)	X	X		X	X	X	X	X	X		
ECHO with interpretation	X										
EKG with interpretation	X										
Anti-drug antibodies (ADA)			X	X	X	X	X		X	X	X
Bone Biomarker Testingd,g											
Formation Testing (bone specific alkaline phosphatase [BAP], type 1 procollagen [P1NP])	-	X				X	X		X		
Resorption testing (C-telopeptide [CTX], Tartrate resistant acid phosphatase type5b [TRAP5b])	-	X				X	X		X		
RANKL, OPG, CK-BB	-	X				X	X		X		
Endocrine Assessment											
Total 25-OH Vitamin D (25OHD)	-	X			X	X	X		X		
Serum ionized calcium	-	X				X	X		X		
Urine calcium: creatinine	-	X				X	X		X		
Intact parathyroid hormone (iPTH)	-	X				X	X		X		
Inflammatory/Immunology											
CBC with differential and platelets	-	X f				X	X		X		
Erythrocyte sedimentation rate (ESR)	-	X f				X	X		X		
Immunologic phenotyping (CD3, 4, 8, 14, 15, 16, 19, 34, 56) g	-	X				X	X		X		
Neuropsychological testing											
Pain assessment	-	X				X	X		X		
Quality of life survey	-	X				X	X		X		
Orthopedic assessment											
Dual energy X-ray absorptiometry (DXA) lumbar spine, total body, total hip and femoral neck (adults $\geq$ 18yrs only)	-	X				-	-		X		
Peripheral Quantitative CT (pQCT) left tibia	-	X				-	X		X		
In vitro osteoclast function assays – [name] Labh											
Gene expression – osteoclast marker genes	-	X				X	X		X		
Osteoclast activity – ability to release calcium phos from coated plate	-	X				X	X		X		
Infectious outcomes											
Number of hospitalizations in prior 3 months	-	X f				X	X		X		

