Number of days treated with antibiotics in last 3 months	-	X f				X	X		X		
Type of infectious organism	-	X f				X	X		X		
Summary of samples collected per visit											
Serum (red top)	1	4	1		1	4	4		4	1	1
Plasma (purple top)	-	5	-		-	5	5		5	-	-
Urine (non-sterile)	1	1	-		-	1	1		1	-	-
Whole blood		1				1	1		1		

RANKL=Receptor activator of nuclear factor kappa-B ligand; OPG=osteoprotegerin; CK-BB=creatinine kinase isoenzyme BB.

a Screening visit evaluations will count for baseline evaluations where applicable.b Genetic testing for CLCN7, CAII, TCIRG1, OSTM1, and RANKL mutations will be done at the University of Minnesota if not already performed clinicallyc Subjects will be contacted on a weekly basis either by email or telephone to monitor safety during the initial 4 week dose escalation period.d Sample collection will be postponed if needed to ensure collection is more than 2 weeks since last fever ( $>100.4^{\circ}\text{F}$  [ $38^{\circ}\text{C}$ ] axillary) or fracture.e Post-menarchal females.f Height (for subjects  $<18$  years), CBC, and ESR will be obtain from the patient's medical record when available and number of hospitalizations and infectious data from the patient's medical record or if not available then the patient's recollection at the baseline visit.g Samples batch shipped every 3 months to [name]/[name] at UMNh Whole blood shipped overnight to [name] at UMN

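### Appendix B tells sites to batch-ship immunophenotyping blood every 3 months, but Section 6.2.3 requires Harbor-UCLA tubes to arrive within 36 hours, so the schedule puts those CD-marker data at risk

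*Combined protocol and SAP*

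**What the plan says.** Appendix B marks the phenotyping row with footnote g: "Immunologic phenotyping (CD3, 4, 8, 14, 15, 16, 19, 34, 56) g". The footnote reads "Samples batch shipped every 3 months to" recipients at the University of Minnesota. The same letter is on the biomarker block: "Bone Biomarker Testing d,g". Footnote h, which calls for overnight shipment of whole blood, is attached only to the in vitro osteoclast assays.

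Section 6.2.3 covers "Whole blood for immunologic phenotyping, genetic testing, and ex vivo assays by" the Minnesota laboratory, limited to blood collected at Harbor-UCLA. It says this blood "will be shipped at ambient temperature by Fed Express overnight" and adds "Ship for arrival within 36 hours of collection to" the Minnesota address. Section 6.2.2 sends the phenotyping tube according to those instructions. Table 2 lists phenotyping as whole blood and answers no in the column on batching at the end of the study. Section 6.3.2 places the assay at the University of Minnesota.

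For bone biomarkers, Section 6.2.3 keeps samples frozen at each site "until the end of the study at which time all samples will be shipped/transported", and Table 2 marks them as batched at study end.

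Section 7.2.2 tests secondary endpoints, immune function among them, from baseline to 12 months by paired t-test or chi-squared. It names no variable for immune function.

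**The concern.** A coordinator at Harbor-UCLA who works from the schedule of events would hold phenotyping tubes for a quarterly shipment. Because footnote h is absent from that row, the schedule also suggests that this blood does not go overnight. Section 6.2.1 provides frozen storage for serum, plasma and urine, and no section describes how to hold whole blood for phenotyping. The footnote thus directs a delay for which the protocol makes no provision.

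At stake are the CD-marker results of Harbor-UCLA subjects. A pre-treatment sample cannot be redrawn once treatment has begun. If a subject's baseline or month-12 value is lost, that subject drops out of any paired comparison of these markers, in a trial that plans 10 subjects.

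**Working it through.** The plan states no figure on this point, so there is none to reproduce. The check sets the instructions side by side and then gives the scale.

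**Phenotyping blood**

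| Place | Instruction | Compatible with footnote g? |
|---|---|---|
| Appendix B, footnote g | Batch to Minnesota every 3 months | – |
| Section 6.2.3 | Harbor-UCLA blood: overnight, ambient, arrival within 36 hours of collection | No |
| Section 6.2.2 | Send by the instructions that follow, i.e. 6.2.3 | No |
| Table 2 | Not batched at end of study | Not literally in conflict: the column asks only about end-of-study batching |
| Table 1 | No shipping note on this row (its own footnote g concerns anti-drug antibodies) | Silent |

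The contradiction therefore rests on 6.2.3, with 6.2.2 pointing to it. Table 2 fits with 6.2.3 but does not by itself exclude quarterly batching.

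**Size of the conflict**

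- Batch interval: 365.25 / 4 = 91.3 days, and 91.3 × 24 ≈ 2,190 hours.
- Ratio to the limit: 2,190 / 36 ≈ 61.
- Assume that draws fall evenly over the interval. The mean wait is 91.3 / 2 ≈ 46 days. The share of tubes drawn within 36 hours of dispatch is 36 / 2,190 ≈ 1.6%. This is an upper bound on the share meeting the limit, because the 36 hours run to arrival and transit uses part of them.

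**Number of samples and pairs**

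Phenotyping is scheduled at 4 visits (baseline, months 3, 6 and 12), so 10 subjects give 10 × 4 = 40 samples. Only Harbor-UCLA samples are shipped under this rule. With H subjects at Harbor-UCLA, 4 × H samples are exposed. Of these, 2 × H (baseline and month 12) enter the Section 7.2.2 comparison, which makes H pairs. The site split is not given, so the table shows the range.

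| H (assumed) | Samples exposed | Baseline and month-12 samples exposed | Pairs exposed | Pairs not exposed |
|---|---|---|---|---|
| 0 | 0 | 0 | 0 | 10 |
| 5 | 20 | 10 | 5 | 5 |
| 10 | 40 | 20 | 10 | 0 |

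These counts assume that all 10 subjects are enrolled and complete month 12.

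**Bone biomarkers**

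Footnote g ships every 3 months; 6.2.3 and Table 2 hold the samples to study end. The instructions differ, but the samples are kept at -80°C. Quarterly shipment of frozen samples could still be followed by one assay run at the end. No effect on a result follows from the text.

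**The case against.** The strongest reply is that the right instruction is already present and more detailed. Section 6.2.3 gives temperature, courier, time limit, delivery days and advance notice, and the version history shows that 6.2.2 and 6.2.3 were revised in version 1.8. The ex vivo tube from the same visits goes out overnight under the same paragraph, so staff who follow the handling section would ship correctly. That lowers the chance of error but does not remove the contradiction: a site schedule that contradicts the handling section is still a defect, and nothing says which prevails.

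One might also read the 3-month interval as meaning that each visit's tubes leave together. This fits poorly with the visit schedule, which has no phenotyping draw between months 6 and 12, and with the separate overnight footnote.

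A reader might infer that following the schedule would lose the immune-function endpoint. The documents do not support this, for three reasons.

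- Immune function is never defined as the CD panel. The hypotheses in Section 4.2 do not list phenotyping. They list blood counts, ESR, hospitalizations for infection and antibiotic days, and none of these depends on footnote g.
- The 36-hour rule covers Harbor-UCLA blood. Minnesota subjects' samples are assayed at Minnesota and are not reached by it.
- No passage says that a late tube is unusable or will be rejected. That is an inference from the protocol's own limit, and a reasonable one, but the claim should stop at data being at risk.

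**Conclusion.** The point holds in a limited form. Footnote g and Section 6.2.3 give incompatible shipping rules for Harbor-UCLA phenotyping blood, and following the footnote would make nearly all of those tubes miss the protocol's own time limit. Their CD-marker data would be put at risk: up to 4 samples per Harbor-UCLA subject, of which 2 matter for a baseline to month-12 comparison, and between 0 and 10 pairs in all.

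The 1.6% figure rests on evenly spread draws, and the pair counts rest on an unstated site split with full enrollment and completion. Loss of a whole endpoint is not shown. The bone biomarker conflict is a consistency error only. Correction is still worthwhile, because a baseline specimen cannot be replaced and the remedy costs almost nothing.

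**What to change.** In Appendix B, remove footnote g from the phenotyping row. Replace it with a new footnote stating that Harbor-UCLA whole blood ships overnight at ambient temperature, for arrival within 36 hours of collection, to the recipients in Section 6.2.3, and cross-refer to that section. Do not simply attach footnote h. It names a single recipient for the osteoclast assays, while Section 6.2.2 gives a pair of recipients for phenotyping; the names are removed, so it cannot be confirmed that the destinations are the same.

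For the bone biomarker block, replace footnote g with wording that agrees with Section 6.2.3 and Table 2: stored at -80°C at each site and batched at study end. If quarterly shipment is in fact intended, change those two places instead.

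The cost is a footnote correction and a notice to the sites. Visits, samples and analyses do not change.
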